### **5.2.3 Reasons for Withdrawals and Discontinuation of Study Product Administration**

Subjects may voluntarily withdraw their consent for trial participation at any time and for any reason, without penalty or loss of benefits to which they are otherwise entitled.

The site PI or appropriate sub-investigator may also withdraw a subject from receiving the study vaccine for any reason.

A subject may withdraw or be withdrawn from this trial for any of the following reasons:

- Medical disease or condition, or any new clinical finding for which continued participation, in the opinion of the site PI or appropriate sub-investigator, would compromise the safety of the subject, or would interfere with the subject's successful completion of this trial, or would interfere with the evaluation of responses (for example, has baseline significant laboratory abnormalities).
- Subject withdrawal of consent.
- Subject lost to follow-up.
- Termination of this trial.

- As deemed necessary by the site PI or appropriate sub-investigator for noncompliance or other reasons.
- New information becomes available that makes further participation unsafe.

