#### **5.2.4 Handling of Withdrawals and Discontinuation of Study Product Administration**

The primary reason for withdrawal from this trial will be recorded on the Study Status data collection form (DCF). Subjects will be encouraged to complete the Early Termination Visit. The Early Termination Visit procedures are listed in [Section 8.4](#).

Every attempt will be made to follow all AEs, including solicited injection site and systemic reactions, unsolicited non-serious AEs, SAEs, AESIs (including Protocol Specified AESIs, MAAEs, NOCMCs and PIMMCs) ongoing at the time of early withdrawal through resolution as per applicable collection times defined for the specific type of AE.

In the case of subjects who fail to appear for a follow-up safety assessment, extensive effort (i.e., three documented contact attempts via phone calls made on separate occasions and followed by a certified letter) will be made to locate or recall them, or at least to determine their health status. These efforts will be documented in the subject's study records.

The site PI or appropriate sub-investigator will inform the subject that already collected data will be retained and analyzed even if the subject withdraws or is withdrawn from this study.

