### **7.2.1 Clinical Laboratory Evaluations**

Urine or serum pregnancy tests will be performed locally by the site at the screening visit (optional) and within 24 hours prior to first study vaccination for all women of childbearing potential. Results must be negative and known prior to randomization on Day 1 and administration of first study vaccination to be eligible for participation in this trial and receipt of study vaccination.

The ESR evaluation will be performed locally by the site at the screening visit and confirmed as less than 30 mm per hour to be eligible for participation in this trial and receipt of the first study vaccination.

Clinical safety laboratory parameters (WBC, Hgb, PLT, ALT, AST, GGT, ALP, Bilirubin (total), serum lipase and serum amylase and Cr) will be collected at the screening study visit and will be sent to the Central Clinical Laboratory. The results from the clinical safety laboratory parameters collected at the screening visit must be reviewed prior to the first study vaccination and must be

within acceptable ranges to be eligible for receipt of the first study vaccination (see [Section 5.1.1](#)). The safety laboratories will be repeated prior to receipt of the first study vaccination. However, the results from the clinical safety laboratory parameters collected prior to the study vaccination will not be available or reviewed prior to the study vaccination. Clinical safety laboratory parameters collected immediately prior to the first study vaccination will serve as the baseline and will be repeated on approximately Day 8.

The volume of venous blood to be collected for ESR and clinical safety laboratory evaluations is presented in [Table 3](#).

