**Table 3: Venipuncture Volumes**

Study Visit Number	V00	V01	V02	V03	V04	V05	V06	V07	V08	V09	Cumulative Blood Volume Total (mL)
Study Day post first study vaccination	Screening D-28 to -1	Enrollment Dose 1 D1	D2 +1	D8+/-1d	D29+/-2d	D57+/-3d	D90 +/-14 d	D118 +/-3 d	D180 +/- 14d	D365-14/+35d	
Study Vaccination		X					X				
ESR	4 ^										4
Clinical Safety Laboratory Evaluations	6 ^	6 #†		6							18
Serological Assays		20 †		20	20	20	20 †	20	20	20	160
Cellular Immunology Assays		80 †		48	80		48 †				256
Tempus RNA Tube		3 †	3	3							9
Per Visit Blood Volume Total (mL)	10	109	3	77	100	20	68	20	20	20	
Running Blood Volume Total (mL)	10	119	122	199	299	319	387	407	427	447	447

^ Drawn up to 28 days prior to the first study vaccination. The ESR value must be confirmed as less than 30 mm per hour prior to randomization and prior to first study vaccination. Screening WBC, Hgb, PLT, ALT, T. Bili, AST, GGT, ALP and serum lipase and serum amylase and Cr must be within the accepted ranges outlined in the inclusion criteria prior to randomization and study vaccination.

# Clinical safety laboratory evaluations collected on Day 1 prior to first study vaccination will be considered as baseline.

† Blood must be drawn immediately prior to each study vaccination.

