#### **14.6 Study Discontinuation**

If this trial is prematurely terminated by the sponsor, any regulatory authority, the site PI, or appropriate sub-investigator for any reason, the site PI or appropriate sub-investigator will promptly inform the subjects and assure appropriate therapy or follow-up for the subjects, as necessary. The site PI or appropriate sub-investigator will provide a detailed written explanation of the termination to the IRB. If any subject's private information will continue to be collected for this trial, the IRB must approve an ICF with the study procedures, any risks and discomforts as well as applicable elements, and the site PI or designee will re-consent the subjects as approved by the IRB.

If this trial is discontinued, subjects, who have signed the ICF, and are randomized and vaccinated, will continue to be followed for safety for the duration of the prescribed safety follow-up period. No further study vaccinations will be administered.

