9.3.2. Unsolicited Adverse Events

When calculating the incidence of unsolicited AEs (i.e., on a per subject basis), each subject will only be counted once at the highest severity and/or relationship, and any repetitions of AEs within a subject will be

ignored; the denominator will be the total number of subjects in the safety population. All AEs reported will be included in the summaries and analyses.

A summary of all unsolicited adverse events by MedDRA SOC, PT, and study arm that occurred from Day 1 to Day 365 is provided in [Table 124](#). Similarly, a summary of all unsolicited adverse events by MedDRA SOC, PT, and study arm that occurred from Day 1 to Day 29 is provided in [Table 125](#).

The number and percentage of subjects reporting at least one unsolicited AE will be summarized by MedDRA system organ class and preferred term. A 95% CI will be presented for the percentage of subjects reporting any unsolicited AE (serious or non-serious) for each MedDRA system organ class and preferred term over all study vaccinations ([Table 126](#)). A similar table summarizing all unsolicited events from Day 1 to Day 29 will be provided ([Table 127](#)).

The following summaries for unsolicited AEs will be presented by MedDRA system organ class, preferred term, and study arm:

- Incidence of AEs by severity and relationship to study product ([Table 128](#));
- Incidence of AEs from Day 1 to Day 29 by severity and relationship to study product ([Table 129](#));
- Incidence of non-serious, related AEs by severity ([Table 130](#));
- Incidence of AEs over time (Days 1-8, Days 9-29 post first study vaccination) ([Table 131](#));
- Incidence of non-serious, related AEs over time (Days 1-8, Days 9-29 post first study vaccination) ([Table 132](#));
- Total frequency of AEs over time (Days 1-8, Days 9-29 post first study vaccination) ([Table 133](#));
- Subject listing of non-serious AEs of moderate or greater severity ([Table 138](#));
- Bar chart displaying total frequency of AEs by severity and MedDRA system organ class and study arm ([Figure 98](#));
- Bar chart displaying incidence of AEs by severity and MedDRA system organ class, and study arm ([Figure 99](#));
- Bar chart displaying total frequency and incidence of AEs by relationship to study product, MedDRA system organ class, and study arm ([Figure 100](#) and [Figure 101](#)).

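### An investigator may withdraw a vaccinated subject from the trial (Protocol 5.2.3), after which only ongoing events are followed (5.2.4): new SAEs and AESIs to month 12 are not actively collected, yet the subject stays in the denominator

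*Protocol*

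**What the plan says.** Protocol 5.2.3 gives two separate powers. The first is to stop study vaccine for any reason. The second is wider: "A subject may withdraw or be withdrawn from this trial for any of the following reasons". The list includes a medical condition or "any new clinical finding for which continued participation, in the opinion of the site PI or appropriate sub-investigator", would endanger the subject, hinder completion of the trial, or "would interfere with the evaluation of responses (for example, has baseline significant laboratory abnormalities". Noncompliance and other reasons are also listed. Neither power is confined to the period before vaccination.

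The note to Protocol Table 3 fixes the meaning of baseline for laboratory tests: "Clinical safety laboratory evaluations collected on Day 1 prior to first study vaccination will be considered as baseline". Protocol 7.2.1 says the results of that draw "will not be available or reviewed prior to the study vaccination".

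For a withdrawn subject, Protocol 5.2.4 encourages an Early Termination Visit and promises every attempt to follow AEs, SAEs and AESIs "ongoing at the time of early withdrawal through resolution". Protocol 14.6 covers a different case, discontinuation of the whole trial: subjects who were randomized and vaccinated "will continue to be followed for safety for the duration of the prescribed safety follow-up period".

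On the analysis side, the Safety Population is everyone who received the first vaccination (Protocol 11.6.1, SAP 6.3.1). For unsolicited AEs, SAP 9.3.2 says "the denominator will be the total number of subjects in the safety population". SAP Table 124 covers Day 1 through Day 365 and describes its N as the subjects at risk.

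**The concern.** SAEs through about 12 months are a primary safety outcome, and AESIs, including NOCMCs and PIMMCs, are a secondary one. Both need surveillance for events that have not yet begun. Under 5.2.3 and 5.2.4 a subject can receive an adjuvanted vaccine, be withdrawn by the investigator a few weeks later, and from then on be followed only for what is already open. An SAE or PIMMC starting at month 5 would be recorded only if the site happened to hear of it. The tables would still count the subject in the Day 1 to Day 365 denominator without an event.

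If the trigger is a clinical finding after dosing, the withdrawal may be related to later risk, so the missing follow-up may not be missing at random. One unseen event matters in this trial: a single related SAE or a single PIMMC is a halting event under Protocol 9.5.2, and Section 2.1 says this is the first human use of an Advax-CpG formulation containing CpG55.2. Withdrawal before Day 29 can also cost the primary titer, since Protocol 11.6.6 and SAP 6.5 impute nothing.

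**Working it through.** **1. Can the rule reach dosed subjects?** Yes. 5.2.3 contains no time limit. If baseline in its laboratory example has the Table 3 meaning (Day 1, before the dose), the results arrive after dosing by 7.2.1, so the example then applies only to vaccinated subjects.

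**2. What is collected afterwards?**

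| Event | Text | Collected? |
|---|---|---|
| Ongoing at withdrawal | 5.2.4; 9.4 (to resolution, even past 12 months) | Yes |
| Began between the last visit and withdrawal | 8.4, Early Termination Visit | Yes, if the subject attends |
| Begins after withdrawal, up to month 12 | None for an investigator-withdrawn subject | No commitment |
| Related SAE the site learns of after trial completion | 9.3.1 | Passive only |

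The third row is the gap. Section 14.6 closes it only when the whole trial is discontinued.

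**3. The plan's own detection figure.** Table 10 gives the chance of at least one event, 1 − (1 − p)^n. At p = 1%:
- n = 40: 1 − 0.99^40 = 33.1% (Table 10: 33)
- n = 240: 1 − 0.99^240 = 91.0% (Table 10: 91)

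**4. Loss unrelated to risk.** The numbers withdrawn are assumptions. The protocol allows for up to 3% dropout by Day 29 and gives no 12-month rate. Treat withdrawn subjects as contributing nothing, which overstates the loss:
- 1, 2 or 4 of 40 lost: 1 − 0.99^39 = 32.4%, 1 − 0.99^38 = 31.7%, 1 − 0.99^36 = 30.4%
- 8 or 24 of 240 lost: 90.3% or 88.6%

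**5. Informative loss.** Suppose w of 40 are withdrawn and their event rate is r times 1%. Full follow-up would detect at least one event with probability 1 − 0.99^(40−w) × (1 − 0.01r)^w; without later follow-up the probability is 1 − 0.99^(40−w).
- w = 2: 31.7%, against 38.4% (r = 5) to 44.7% (r = 10)
- w = 4: 30.4%, against 43.3% (r = 5) to 54.3% (r = 10)

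The multipliers 5 and 10 are assumptions; the documents give none.

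**6. One missed event.** Clopper-Pearson 95% intervals for n = 40: 1/40 gives 0.06% to 13.2% and 0/40 gives 0% to 8.8%. So if one withdrawn subject had a later SAE that went unseen, the arm's upper limit would read 8.8% instead of 13.2%. This shows what one missed event does, not how likely it is.

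**The case against.** A reader might infer that 12-month SAE follow-up simply ends on withdrawal, and ends for the subjects most likely to carry a signal. The documents do not support that.

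- **The trigger is not lost.** If the new finding is itself an AE, SAE or AESI, it is recorded and followed to resolution. Only a later, separate event is at risk.
- **Day 1 laboratory values carry no adjuvant signal.** They are drawn before exposure, in randomized subjects with blinded assessors. The wording may not even mean Day 1: Protocol 9.2.1 calls conditions present at screening baseline, and 5.2.5 foresees withdrawal before vaccination.
- **The gap is silence, not an instruction to stop.** Trial termination is itself on the 5.2.3 list, and 14.6 keeps those subjects in safety follow-up, so withdrawal and safety follow-up can coexist. Footnotes 3 and 4 of Appendix A refer to subjects being followed for safety.
- **Attrition is visible.** Protocol 11.6.2 and SAP 9.4 report SAEs and AESIs mainly as listings. SAP Table 13 shows Day 365 completion by arm, Listing 2 gives reason and study day, and Table 117 counts AEs leading to early termination.
- **The power is discretionary,** and its expected use is unknown.

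All of this narrows the point, and the argument about Day 1 values stands in full. None of it supplies surveillance for events starting after an investigator withdrawal: the safety-follow-up status in Appendix A is never assigned to such a subject, and disclosing attrition does not recover the events.

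**Conclusion.** The point holds in a limited form. The protocol permits investigator withdrawal of a vaccinated subject from the trial, promises afterwards only to follow ongoing events, and leaves the subject in a Day 1 to Day 365 denominator. Section 14.6 takes a fuller approach for a discontinued trial, and nothing explains the difference.

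The size is unknown. With loss unrelated to risk it is small: 33.1% to 31.7% for 2 of 40 at a 1% rate. It becomes material only if withdrawn subjects have a clearly raised later event rate, which is plausible for post-dose findings but is an assumption. A reader might also infer a downward bias in SAE proportions concentrated in a reactogenic arm; the documents give no withdrawal counts by cause or arm to establish that.

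Nor is trial withdrawal needed to protect the per-protocol immunogenicity analysis. The per-protocol definition already drops data from subjects found ineligible at baseline and from visits after major deviations. This is a worthwhile, inexpensive improvement rather than a flaw that undermines the trial.

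**What to change.** Reconcile Protocol 5.2.3, 5.2.4 and 14.6, with a matching line in 8.4. State that a vaccinated subject whom the investigator takes off further study vaccination or procedures, and who has not withdrawn consent, remains in SAE and AESI follow-up through about Day 365, by telephone if needed, and gives the Day 29 serum if willing. Clarify what baseline means in the laboratory example, or remove it as a reason for leaving the trial after dosing.

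This need not prohibit investigator-initiated withdrawal. Discretion over vaccination and procedures stays as written; only the follow-up afterwards is specified.

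The cost is a sentence or two in each section and a few telephone contacts. No added subjects or assay types are needed, and the SAP denominator can stay as it is, because the time it covers would then be observed for these subjects.

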#### **5.2.4 Handling of Withdrawals and Discontinuation of Study Product Administration**

The primary reason for withdrawal from this trial will be recorded on the Study Status data collection form (DCF). Subjects will be encouraged to complete the Early Termination Visit. The Early Termination Visit procedures are listed in [Section 8.4](#).

Every attempt will be made to follow all AEs, including solicited injection site and systemic reactions, unsolicited non-serious AEs, SAEs, AESIs (including Protocol Specified AESIs, MAAEs, NOCMCs and PIMMCs) ongoing at the time of early withdrawal through resolution as per applicable collection times defined for the specific type of AE.

In the case of subjects who fail to appear for a follow-up safety assessment, extensive effort (i.e., three documented contact attempts via phone calls made on separate occasions and followed by a certified letter) will be made to locate or recall them, or at least to determine their health status. These efforts will be documented in the subject's study records.

The site PI or appropriate sub-investigator will inform the subject that already collected data will be retained and analyzed even if the subject withdraws or is withdrawn from this study.

#### **5.2.5 Subject Replacement**

Subjects who withdraw, or are withdrawn or terminated from this trial, or are lost to follow-up after signing the informed consent form (ICF), randomization and receipt of study vaccine will not be replaced. However, if a subject withdraws after signing the ICF, but before randomization and/or receipt of study vaccine, they may be replaced.

#### **5.2.6 Termination of Study**

Although the sponsor has every intention of completing this trial, it reserves the right to terminate this trial at any time for clinical or administrative reasons. Reasons for termination include, but are not limited to, study closure due to DSMB review and recommendation, and at the discretion of DMID.

If this trial is prematurely terminated by the sponsor, any regulatory authority, the site PI, or appropriate sub-investigator for any reason, the site PI or appropriate sub-investigator will promptly inform the subjects and assure appropriate therapy or follow-up for the subjects, as necessary. The site PI or appropriate sub-investigator will provide a detailed written explanation of the termination to the IRB.

## **6 STUDY INTERVENTION/INVESTIGATIONAL PRODUCT**

### **6.1 Study Product Description**

#### 2018/2019 and 2019/2020 Fluzone Quadrivalent Influenza Vaccine (QIV)

The Sanofi Pasteur manufactured Fluzone Quadrivalent is an FDA approved vaccine indicated for active immunization in persons 6 months of age and older for the prevention of influenza disease caused by influenza viruses contained in the vaccine. Fluzone QIV is propagated in embryonated chicken eggs, chemically inactivated, disrupted and purified to yield a split virus vaccine.

#### 2018/2019 and 2019/2020 Flublok Quadrivalent Influenza Vaccine (QIV)

The Sanofi Pasteur (Protein Sciences Corporation) manufactured FluBlok Quadrivalent is an FDA approved recombinant HA protein vaccine indicated for active immunization in persons 18 years of age and older for the prevention of influenza disease caused by influenza viruses contained in the vaccine. It contains purified HA proteins produced in a Sf9 insect cell line derived from the fall armyworm, *Spodoptera frugiperda*.

#### 2018/2019 Fluzone and 2018/2019 Flublok Vaccine Expiry

The 2018/2019 Fluzone and Flublok are labeled to expire on June 30, 2019. The expiration date that is present on the label of licensed seasonal influenza vaccine is to ensure the product made for previous years' influenza strains are not still available for general licensed use when new seasonal vaccine becomes available against the most recent circulating strains. Historical data exists indicating that flu vaccine maintains potency for a period well beyond its expiration date. For this clinical trial, the 2018/2019 Fluzone and Flublok will be used beyond the labeled expiration date.

#### AF03 Adjuvant

The Sanofi Pasteur adjuvant formulation AF03 is a squalene-in-PBS emulsion stabilized by non-ionic surfactants, sorbitan oleate and macrogol cetostearyl ether prepared by the "Phase Inversion Temperature" (PIT) method.

#### Advax-CpG55.2 Adjuvant

The Vaxine adjuvant Advax-CpG55.2 is a combination adjuvant supplied as two separate components, Advax (delta inulin) and CpG55.2, in individual aseptic glass vials.

#### Advax (Delta Inulin)

Inulin is a natural storage polysaccharide of plants of the Compositae family, such as dahlias, artichoke and chicory. Inulin exists in different polymorphic forms. Advax is manufactured from highly purified inulin that is subsequently crystallized into microscopic particles of known as delta inulin and then formulated in an aqueous phosphate buffer. Advax adjuvant appears as a milky white non-viscous suspension and if left undisturbed on a stable surface for several days to weeks the delta inulin particles will slowly sediment to the bottom of the vial, leaving a clear slightly off white solution above them. The particles can be resuspended easily by simple repeated inversion of the vial several times.

#### CpG55.2

CpG55.2 is a completely synthetic Class B CpG oligonucleotide of 24 nucleotides in length with a full phosphorothioate backbone for increased stability. It is presented as a clear solution in an aqueous buffer.

#### Acquisition

2018/2019 and 2019/2020 Fluzone QIV and Flublok QIV and the AF03 adjuvant will be provided by Sanofi Pasteur.

Advax and CpG55.2 adjuvants, the individual components of Advax-CpG55.2 adjuvant will be provided by Vaxine.

Sterile Water for Injection (SWI) will be provided by DMID Clinical Materials Services Contract.

Upon request by DMID, 2018/2019 and 2019/2020 Fluzone QIV and Flublok QIV, AF03 and Advax and CpG55.2 adjuvants will be transferred to the following address:

DMID Clinical Materials Services Contract  
Fisher BioServices  
[name]  
[name]  
[contact]  
[contact]  
Email: [contact]

2018/2019 and 2019/2020 Fluzone QIV and Flublok QIV, AF03 and Advax and CpG55.2 adjuvants, and SWI for study vaccine preparation will be provided through the DMID CMS to the participating VTEU sites prior to the start of this trial upon request and with prior approval from DMID. Should the site PI require additional 2018/2019 and 2019/2020 Fluzone QIV and Flublok QIV, AF03 and Advax and CpG55.2 adjuvants, or SWI during this trial, contact the DMID CPM.

